8.6.2 Statistical Methods for Safety Analyses

Safety and tolerability will be assessed by clinical review of all relevant parameters including adverse experiences (AEs), laboratory tests and vital signs measurements.

The analysis of safety results will follow a tiered approach (Table 6). The tiers differ with respect to the analyses that will be performed.

Table 6 Analysis Strategy for Safety Parameters

Safety Tier	Safety Endpoint [†]	p-Value	95% CI	Descriptive Statistics
Tier 1 [‡]	Serious infections, serious opportunistic infections, active tuberculosis, malignancies, and serious systemic hypersensitivity (including anaphylactic reaction)	X	X	X
Tier 2	Any AE Any Serious AE Any Drug-Related AE Any Serious and Drug-Related AE Discontinuation due to AE Specific AEs, SOCs or MA lab values (incidence ≥4 subjects in one of the treatment groups)		X X X X X X	X X X X X X
Tier 3	Specific AEs, SOCs or MA lab values (incidence <4 subjects in all of the treatment groups) Change from Baseline Results (Labs, Vital Signs)			X X
[†] Adverse Experience references refer to both Clinical and Laboratory AEs. [‡] Applies to Period 2 only. Note: SOC=System Organ Class; MA=Markedly Abnormal; X = results will be provided.				

Tier 1 analysis will be performed in Period 2 only if there are at least 4 events in one of the treatment arms, using the Miettinen and Nurminen method for between-treatment differences in the percentage of subjects with events. In the case of less than 4 events in each treatment arms, the Tier 1 events will be listed by subject, treatment and period. Other safety parameters will be considered Tier 2 or Tier 3. Tier 2 parameters will be assessed via point estimates with 95% confidence intervals provided; only point estimates are provided for Tier 3 safety parameters. Adverse experiences (specific terms as well as system organ class terms) that are not pre-specified as Tier-1 endpoints will be classified as belonging to "Tier 2" or "Tier 3", based on the number of events observed. Membership in Tier 2 requires that at least 4 subjects in any treatment group exhibit the event; all other adverse experiences and predefined limits of change will belong to Tier 3. For this protocol, broad clinical and laboratory AE categories (consisting of the percentage of subjects with: Any AE, a Drug-related AE, a Serious AE, an AE that is both Drug-related and Serious, and Discontinued due to an AE) will be considered Tier 2 endpoints. Using the exact binomial method of Clopper and Pearson (Period 1) and Miettinen and Nurminen (Period 2), 95% confidence intervals will be provided for the percentages of subjects with events.

The threshold of at least 4 events was chosen because the 95% confidence interval for the between-group difference in percent incidence will always include zero when treatment groups of equal size each have less than 4 events and thus would add little to the interpretation of potentially meaningful differences. Because many 95% confidence intervals may be provided without adjustment for multiplicity, the confidence intervals should be regarded as a helpful descriptive measure to be used in review, not a formal method for assessing the statistical significance of the between-group differences in adverse experiences and predefined limits of change.

Safety data from Period 1 and Period 2 will be summarized separately. Period-2 safety data will be summarized for each treatment group (GLM QM, GLM Q2M, and PBO); in the case of re-treatment, safety data will also be summarized for the time before re-treatment vs. the time after re-treatment.

Continuous measures, such as changes from baseline in laboratory and vital signs parameters, will be considered Tier 3 safety parameters. Summary statistics for baseline, on-treatment, and change from baseline values will be provided by treatment group in table format.

Events of clinical interest will be listed by subject. Other selected safety endpoints of interest will be listed by subject, treatment and period; these endpoints include: serious infections, serious opportunistic infections, active tuberculosis, malignancies, and serious systemic hypersensitivity (including anaphylactic reaction).

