If a “flare” occurs during Period 2, then subjects discontinue blinded therapy (placebo, golimumab QM, or golimumab Q2M) and begin re-treatment with open-label golimumab QM. There should be an interval of at least 10 days between the last dose of Period-2 double-blind therapy and the first dose of open-label golimumab after a “flare” is confirmed. Thereafter, it is expected that re-treatment with open-label golimumab continues monthly through the end of Period 2. A clinical response to re-treatment is defined as a BASDAI score improvement of ≥ 2 or $\geq 50\%$ improvement (measured relative to the mean of the 2 BASDAI scores that were collected at the 2 consecutive assessments that defined the “flare”) that occurs within 3 months of restarting open-label treatment. If a subject shows insufficient improvement after 3 months of restarting open-label treatment for a “flare”, the investigator may consider discontinuing this subject from the study (based on clinical judgment) and will ensure a safety follow-up telephone call 3 months after the last dose of trial medication. If the subject is determined to have experienced a first “flare” between Months 19 and 22, the subject then completes a course of re-treatment (i.e., 3 monthly open-label golimumab injections) and will have a safety follow-up telephone call 3 months after the last dose of open-label golimumab. Subjects who do not experience a “flare” during Period 2 are to complete the study at Month 22 and will have a safety follow-up telephone call 3 months after their last dose of blinded trial medication.

Approximately 300 subjects are expected to enter Period 1. Based on the response to golimumab observed in the recently completed GO-AHEAD trial (P07642) [1], approximately 114 subjects are expected to continue into Period 2, based on attaining inactive disease status (ASDAS < 1.3) at both Months 7 and 10 of open-label golimumab. If the number of subjects who attain inactive disease is fewer than expected, additional subjects may need to enter Period 1 in order to randomize approximately 114 subjects with inactive disease status in Period 2.

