4.3 Benefit/Risk

Golimumab has been shown to be effective and generally safe and well-tolerated in subjects for the treatment of nr-axSpA, and it is currently approved for use in this disease. The risks of golimumab include serious infections (including opportunistic infections and tuberculosis), congestive heart failure, lymphoma (and other malignancies), infusion-related reactions, and other risks as detailed in the current product labeling.

In this trial, subjects who have insufficient benefit from the approved regimen of golimumab, after approximately 4 months of open-label treatment, are to be discontinued from the study, so they can seek alternative therapy. Subjects are also discontinued from the study if they have not attained inactive disease status after either 7 or 10 months of open-label treatment. Subjects who attain inactive disease after both 7 and 10 months of open-label golimumab can then be randomly withdrawn from treatment or continued on treatment using a full regimen (golimumab QM) or a reduced regimen (golimumab Q2M). All randomized subjects are monitored for the risk of a worsening in their disease: subjects are closely followed (using self-ratings of their disease, collected twice monthly) and closely observed (at clinic visits every 2 months). The risk of this investigational treatment paradigm is that subjects may experience worsening of their symptoms upon withdrawal of golimumab and may not respond as effectively to golimumab when it is reinitiated to treat a “flare”.

The benefits of this investigational treatment paradigm are that subjects will receive golimumab at the approved dose and regimen for the first 10 months of the trial and can reasonably expect to experience adequate control of their disease. The trial may demonstrate that control of symptoms is adequate following withdrawal of golimumab for a period of time and that continuous use (whether using a full regimen or a reduced regimen) is not necessary in all subjects. The benefit of this paradigm will be less exposure to golimumab and potentially the reduction in established risks associated with use of a TNF-inhibitor, such as serious infections and malignancies.

Additional details regarding specific benefits and risks for subjects participating in this clinical trial may be found in the accompanying Investigators Brochure (IB) and ICF documents.

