8.1 Statistical Analysis Plan Summary

Key elements of the statistical analysis plan are summarized below; the comprehensive plan is provided in Sections 8.2-8.12.

Study Design Overview	Phase IV, randomized, double-blind withdrawal study to evaluate the efficacy and safety of golimumab (MK-8259, GLM) after treatment withdrawal, compared with continuous treatment (either full- or reduced-treatment regimen), in subjects with nr-axSpA
Treatment Assignment	In Period 1, all subjects receive open-label GLM. In Period 2, subjects who attained inactive disease status (at both Month 7 and Month 10 of open-label golimumab treatment) in Period 1 undergo stratified randomization, in a 1:1:1 ratio (Placebo QM : GLM QM : GLM Q2M).
Analysis Populations	Efficacy : The primary efficacy population is: subjects who are randomized in Period 2 and take at least one dose of trial medication in Period 2. Safety : All Subjects as Treated (ASaT).
Primary Endpoint(s)	Proportion of subjects without a “flare” during up to 12 months in Period 2.
Key Secondary Endpoints	None
Statistical Methods for Key Efficacy Analyses	The primary hypothesis will be evaluated by comparing treatment withdrawal (PBO) versus continued treatment with either GLM QM or GLM Q2M in the proportion of subjects without a “flare”, using a stratified Miettinen and Nurminen (M&N) test.
Statistical Methods for Safety Analyses	Percentages of subjects with AEs in Period 2 will be summarized, using 95% CIs based on the M&N method, for broad AE categories (subjects with: Any AE, a Drug-related AE, a Serious AE, an AE that is both Drug-related and Serious, and Discontinuation due to AE).
Interim Analyses	No interim analysis is planned.

Multiplicity	The Type-I error rate over the multiple treatment comparisons will be controlled by a sequential (step down) testing procedure.

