8.5.2 Safety Analysis Populations

Period 1 safety data will be analyzed separately from Period-2 safety data.

Period 2: The ASaT population consists of all Period 2 randomized subjects who receive at least one dose of post-randomization study treatment.

At least one laboratory or vital sign measurement obtained subsequent to at least one dose of study treatment is required for inclusion in the analysis of each specific parameter. To assess change from baseline, a baseline measurement is also required.

Subjects will be included in the treatment group corresponding to the study treatment they actually received for the analysis of safety data using the ASaT population. For most subjects this will be the treatment group to which they are randomized. Subjects who take incorrect study treatment for the entire treatment period will be included in the treatment group corresponding to the study treatment actually received.

Details on the approach to handling missing data for safety analyses are provided in Section 8.6 Statistical Methods.

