8.9 Sample Size and Power Calculations

A total of approximately 300 subjects will be enrolled. Assuming the proportion of subjects who attain inactive disease in Period 1 at both Months 7 and 10 is about 38% (based on the GO-AHEAD study, P07642 [1]), 300 enrolled subjects would result in approximately 114 subjects eligible for Period 2 of the study. With 114 subjects randomized in a ratio of 1:1:1 into the PBO, GLM QM, and GLM Q2M arms, 38 subjects are expected in each treatment arm.

Based on an expected proportion who do not “flare” of 80% in the GLM QM arm (based on study P07642) and 30% in the PBO arm (based on studies of subjects with early axial spondyloarthritis [7]), the power to detect a difference between treatment withdrawal (PBO) vs. continued treatment with GLM QM in the proportion of subjects who do not “flare” exceeds 99%, given $\alpha=0.05$ (2-sided). (See the bold text in Table 6 below.) If the primary hypothesis is rejected for the GLM QM vs. PBO (treatment withdrawal) comparison, then tests of GLM Q2M vs. PBO will be conducted. It is not known if the proportion who do not “flare” for the GLM Q2M arm will be similar to that for the GLM QM arm; but with a sample size of 38 per arm, the study will have 88% power to detect differences of 75% vs. 40% in the proportions of subjects who do not “flare”, should the estimates of absence of “flare” differ from what has been observed in prior studies [7]. (See the bold italic text in [Table 7](#) provides estimates of power for several response scenarios.

Table 7 Power for the Primary Endpoint, Comparing Two Treatment Arms

Treatment withdrawal: Placebo arm	Continued golimumab: QM or Q2M arm	
Proportion who Do not “flare” (N=38)	Proportion who Do not “flare” (N=38)	Power†
20%	80%	99%
	75%	99%
	70%	99%
	65%	98%
	60%	96%
30%	80%	99%
	75%	98%
	70%	95%
	65%	87%
	60%	75%
40%	80%	96%
	75%	88%
	70%	75%
	65%	59%
	60%	41%
†Assumes $\alpha=0.05$ and 2-sided test QM=every month; Q2M=every 2 months		

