8.12 Extent of Exposure

The Extent of Exposure to study treatment will be evaluated by summary statistics (N, mean, median, and standard deviation) for the “Number of Days on Therapy” by Period and treatment group. A summary of total GLM exposure across Periods 1 and 2 will also be provided.

Period-2 duration of exposure will be calculated as follows:

- GLM QM group = the number of days from the first dose of GLM at Month 10 to the last dose + 30 days;
- GLM Q2M group = the number of days from the first dose of GLM at Month 10 to the last dose of GLM + 30 days;
- Placebo (withdrawal) group = number of days from Month 10 to the first dose of GLM given as re-treatment for a “flare” or to study discontinuation for subjects who don’t undergo re-treatment with GLM.

Due to the long half-life of GLM, the above subject-time computations will ignore the missing doses. The total subject-time of exposure for a group will be the sum of the subject-time of exposure of all subjects in the group.

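### Period-2 safety is planned only as percentages of subjects; before re-treatment this favours placebo for common events, because placebo subjects are expected to be observed for less time

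*Combined protocol and SAP*

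**What the plan says.** Section 8.6.2 analyses Tier-1 events in Period 2 "using the Miettinen and Nurminen method for between-treatment differences in the percentage of subjects with events", provided one arm has at least 4 events. Table 6 gives Tier 1 a p-value and a 95% interval, and Tier 2 a 95% interval. The summary in Section 8.1 agrees: "Percentages of subjects with AEs in Period 2 will be summarized, using 95% CIs based on the M&N method". Period-2 safety is presented by treatment group, and "in the case of re-treatment, safety data will also be summarized for the time before re-treatment vs. the time after re-treatment".

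On a confirmed flare, "subjects discontinue blinded therapy (placebo, golimumab QM, or golimumab Q2M) and begin re-treatment with open-label golimumab QM" (Section 2.1). Section 8.5.2 has one regrouping rule: "Subjects who take incorrect study treatment for the entire treatment period will be included in the treatment group" they actually received. A placebo subject who switches at a flare therefore stays in the placebo group.

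Section 8.12 does sum subject-time, but only to describe exposure. The placebo clock is the "number of days from Month 10 to the first dose of GLM given as re-treatment", or to discontinuation if there is no re-treatment. The QM and every-2-months (Q2M) clocks run to the last dose plus 30 days, with no stop at re-treatment stated. The matters left to a supplemental SAP include exploratory objectives, Period 1 analyses, imputation details, antibodies and pharmacokinetics. Period-2 adverse events are not named among them.

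**The concern.** A percentage of subjects with an event compares arms fairly when they are observed for similar lengths of time. Before re-treatment they will not be, if the primary hypothesis is right: more placebo subjects flare, and their time in that window then ends. With identical AE hazards, fewer placebo subjects will show an event.

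The direction matters because Section 4.3 states the case for withdrawal in these terms: "The benefit of this paradigm will be less exposure to golimumab and potentially the reduction in established risks associated with use of a TNF-inhibitor". Unequal time alone would push the percentages before re-treatment the same way. It would also understate any event that becomes more frequent after withdrawal; Section 7.1.2.11 asks sites to record flares of uveitis, psoriasis and inflammatory bowel disease.

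Over all of Period 2 by assigned arm, observation time is similar, but the placebo column then mixes time off golimumab with time on open-label golimumab.

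**Working it through.** **Inputs from the plan.** Section 8.9 assumes an "expected proportion who do not “flare” of 80% in the GLM QM arm (based on study P07642) and 30% in the PBO arm", with 75% vs 40% as an alternative, and 38 subjects per arm. These figures reproduce: 300 × 0.38 = 114 and 114/3 = 38. A two-proportion test with 38 per arm has power 99.7% for 80% vs 30% (plan: above 99%) and 88.6% for 75% vs 40% (plan: 88%).

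**Assumptions not in the documents.** Flare timing (a constant hazard unless stated), 12-month AE rates, and the golimumab hazard ratio in step 4.

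**1. Time before re-treatment.** For flare-free proportion S, let H = −ln S. Mean months = 12(1 − S)/H.
- Placebo, S = 0.30: 12 × 0.70/1.204 = 6.98
- QM, S = 0.80: 12 × 0.20/0.2231 = 10.76

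For 38 subjects this is 22.1 vs 34.1 subject-years, a ratio of 1.54. Flare timing was varied: no flares in the first 2 or 4 months, flares uniform over 12 months, or all flares at month 3. The ratio then runs from 1.29 to 1.79. At 40%/75% it is 1.33 (range 1.19 to 1.48).

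**2. Percentage with an event before re-treatment, same AE hazard in both arms.** For 12-month AE rate p, let A = −ln(1 − p). The percentage is A/(A + H) × [1 − (1 − p)S].
- Placebo, p = 0.40: 0.5108/1.7148 × (1 − 0.60 × 0.30) = 24.4%
- QM, p = 0.40: 0.5108/0.7340 × (1 − 0.60 × 0.80) = 36.2%

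| 12-month AE rate | Placebo vs QM at 30%/80% flare-free | Placebo vs QM at 40%/75% flare-free |
|---|---|---|
| 5% | 2.9% vs 4.5% | 3.3% vs 4.4% |
| 10% | 5.9% vs 9.0% | 6.6% vs 8.7% |
| 40% | 24.4% vs 36.2% | 27.2% vs 35.2% |
| 80% | 53.8% vs 73.8% | 58.6% vs 72.1% |

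**3. The same data as a rate.** Mean time to first event, flare or month 12 is 12[1 − (1 − p)S]/(A + H). At p = 0.40:
- Placebo: 12 × 0.82/1.7148 = 5.74 months, so 0.244/(5.74/12) = 0.51 per subject-year
- QM: 12 × 0.52/0.7340 = 8.50 months, so 0.362/(8.50/12) = 0.51 per subject-year

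Both are about 51 per 100 subject-years, so the artefact is gone. In 20,000 simulated trials with equal hazards, the 95% interval for the rate ratio excluded 1 in 4.4% to 5.4% (AE rates 40% to 80%).

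**4. All of Period 2 by assigned arm.** Placebo time on open-label golimumab is 1 − 6.98/12 = 42%, or 15.9 of 38 subject-years (10.6 to 20.0 across the timing assumptions). Suppose golimumab doubles an AE hazard, with 40% affected on QM (A₁ = 0.5108). Off drug the hazard is halved (A₀ = 0.2554), giving 1 − √0.60 = 22.5%. For placebo with a switch at flare, the probability of no event is S·e^(−A₀) + H·e^(−A₁)·(1 − e^(−(H + A₀ − A₁)))/(H + A₀ − A₁) = 0.232 + 0.467 = 0.699. The placebo arm shows 30.1%, and a 17.5-point difference appears as 9.9.

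**The case against.** The strongest reply is that the plan attaches its between-arm method to Period 2, while the split at re-treatment is written as a summary. No between-arm test or interval is clearly assigned to the window where time is most unequal. Over all of Period 2 the by-arm comparison is sound for assigned strategies, and the dilution follows from the design. This stands.

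Section 8.6.2 also calls the intervals descriptive. Its stated reason is multiplicity, not unequal time, but it does mean that no formal error rate is claimed for Tier 2. Where p-values are planned, the events are mostly rare and the distortion is small. This stands too.

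Flare timing is not in the documents. The last open-label dose at Month 9, the long half-life, the confirmation step and the 10-day gap before open-label dosing all suggest later re-treatment than a constant hazard from the first day. The primary endpoint counts discontinuations as flares, so not every counted flare leads to re-treatment. These facts reduce the size of the effect. Under every timing pattern tried at 30%/80%, placebo still has 2.5 to 4.5 months less.

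Finally, Section 8.12 will report placebo's shorter exposure. That alerts a reader but does not adjust any AE comparison, and its clocks are not aligned across arms.

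**Conclusion.** The point holds as a minor improvement to the safety analysis. Percentages before re-treatment would make placebo look safer for common events at equal hazards, by about 12 points at a 40% AE rate (8 points at 40%/75% flare-free). For rare events the gap is small: 3.1 points at a 10% rate and 1.6 points at 5%. These sizes rest on the plan's flare-free rates, a constant flare hazard and assumed AE rates. No Q2M figure is given, because the plan says its flare rate is unknown.

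Three stronger readings are not supported:
- **Frequent false safety signals.** With Miettinen and Nurminen intervals between arms before re-treatment, placebo would be significantly lower in 20%, 31% and 44% of trials at AE rates of 40%, 60% and 80%, against a nominal 2.5%. With no flares in the first 3 months, the figures are 12%, 17% and 22%. They apply only if such intervals are produced for that window, which the plan does not clearly call for. At a 5% AE rate the figure is 3.1%.
- **An invalid whole-period comparison.** It is valid for strategies. It is only a diluted measure of golimumab against none.
- **A plan that ignores time.** Section 8.12 computes subject-time; the gap is that no AE analysis uses it.

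The primary efficacy analysis is unaffected.

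**What to change.** In Section 8.6.2 and Table 6:

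1. State that the Miettinen and Nurminen comparisons are by assigned arm over all of Period 2. Label the placebo column as including open-label golimumab after a flare.
2. For the time before re-treatment, add subjects with a first event per 100 subject-years, with 95% confidence intervals. Do this for the broad Tier-2 categories, and for Tier 1 where there are enough events.
3. Use one clock in all three arms: from the first Period-2 dose to the first event, the first open-label dose or the end of AE follow-up, whichever comes first.
4. Report the time after re-treatment separately, with its own subject-time.

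The cost is SAP wording and one table, since AE and dosing dates are already collected. The downside is that a rate assumes a roughly constant AE hazard and that leaving at a flare is unrelated to AE risk. The second assumption is least secure for disease-related events such as uveitis. Rare Tier-1 events will remain imprecise.

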At Month 10 (Visit 23; see also Trial Flow Chart – Section 6.1), evaluations are performed to calculate ASDAS. Subjects who have attained inactive disease status (defined as ASDAS < 1.3) at both Months 7 and 10 of open-label treatment are eligible to enter the double-blind withdrawal period (see Section 7.1.5.4 for more details); only these subjects are to be scheduled for the next clinic visit (Visit 24), which begins Period 2. Eligible subjects undergo stratified randomization in a 1:1:1 ratio to one of the following 3 treatment arms: 1) treatment-withdrawal (i.e., monthly injections of matching-placebo for golimumab), 2) golimumab QM (i.e., a full-treatment regimen, per approved labeling), or 3) golimumab Q2M (i.e., a reduced-treatment regimen, via monthly injections that alternate between golimumab and matching-placebo for golimumab). Strata are defined by the presence or absence of elevated CRP (> 6.0 mg/L vs. ≤ 6.0 mg/L) at the Screening visit. Eligible subjects receive their initial dose of blinded trial medication during Visit 24. Subjects who do not have inactive disease at Visit 23 do not enter Period 2; these subjects are discontinued from the study (and will have a safety follow-up telephone call 3 months after their last dose of trial medication).

Over the course of 12 months during Period 2, subjects return to the trial site for evaluation, including laboratory testing, approximately every 2 months (starting from the initial dose of double-blind trial medication). Subjects also continue to complete the BASDAI questionnaire twice monthly in order to rate disease activity. If there is an increase of ≥ 2 (on the 0 to 10 NRS) in BASDAI score compared to Month 10 (Visit 23), the trial site calls the subject to initiate a full evaluation of whether a “flare” (indicative of increased disease activity) is occurring; assessments include information obtained over the phone and/or at an unscheduled visit. A “flare” is defined by ASDAS collected at 2 consecutive assessments that both show absolute score ≥ 2.1 and/or post-withdrawal increase (i.e., change from Visit 23) of ≥ 1.1 (see Section 7.1.5.5 for details on confirming a “flare”).

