8.6 Statistical Methods

Statistical approaches for efficacy analyses are described in Section 8.6.1. Statistical approaches for safety analyses are described in 8.6.2. Ninety-five percent confidence intervals will be generated for response rates of various endpoints as detailed below. Efficacy results that will be deemed to be statistically significant after consideration of the Type I error control strategy are described in Section 8.8, Multiplicity. Unless otherwise stated, all statistical tests will be conducted at the $\alpha=0.05$ (2-sided) level.

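### Period-2 adverse-event percentages before re-treatment rest on unequal time at risk, and no planned adverse-event analysis uses subject-time

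*Combined protocol and SAP*

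**What the plan says.** Section 2.1 sets up three arms ("Eligible subjects undergo stratified randomization in a 1:1:1 ratio"). After a confirmed flare in any arm, "subjects discontinue blinded therapy (placebo, golimumab QM, or golimumab Q2M) and begin re-treatment with open-label golimumab QM". Section 7.2 keeps adverse-event reporting open until 90 days after treatment stops, so events during re-treatment are collected.

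Section 8.6.2 says "Period-2 safety data will be summarized for each treatment group (GLM QM, GLM Q2M, and PBO". The same sentence goes on to plan a further summary of safety before and after re-treatment. Tier 1 events are compared "using the Miettinen and Nurminen method for between-treatment differences in the percentage of subjects with events", with a p-value (Table 6), provided that one arm has at least 4 events. Tier 2 events get 95% intervals. Section 8.1 describes the same approach: "Percentages of subjects with AEs in Period 2 will be summarized, using 95% CIs based on the M&N method". Neither section says whether the whole of Period 2 or only the time before re-treatment feeds the Tier 1 test and the Tier 2 intervals.

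Section 8.5.2 groups subjects by the treatment they received, but it reassigns only those on incorrect treatment throughout. A placebo subject who flares stays in the placebo group.

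Section 8.12 defines exposure per group: "The total subject-time of exposure for a group will be the sum of the subject-time of exposure of all subjects in the group". The placebo clock ends at the first re-treatment dose, or at study discontinuation for those not re-treated. The two golimumab clocks run to the last dose plus 30 days, and no stop at re-treatment is stated. No adverse-event analysis refers to this subject-time.

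**The concern.** A percentage of subjects with an event is comparable between arms only if time at risk is similar. Before re-treatment it will not be. Flare ends a subject's time in that window, and the plan expects far more flares on placebo than on monthly golimumab. Placebo subjects then have less time in which to record a first event, and golimumab looks less safe even if the true rates are equal.

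The whole-Period-2 percentages have roughly equal follow-up, but part of the placebo arm's time is spent on open-label golimumab. They answer a question about strategies and say little about time off drug.

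This matters because Section 4.3 gives lower golimumab exposure, with potentially fewer serious infections and malignancies, as the benefit of the withdrawal paradigm, and characterizing safety is a secondary objective (Section 3.2). A reader who wants to know what happens off drug has only the before-re-treatment percentages, and those are tilted.

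**Working it through.** **Inputs from the documents.** Section 8.9: "38 subjects are expected in each treatment arm"; flare-free proportions of 80% (GLM QM) and 30% (PBO), with 75% and 40% as the second scenario. Section 8.6: "all statistical tests will be conducted at the $\alpha=0.05$ (2-sided) level". Period 2 lasts about 12 months (Section 2.1). The documents give no adverse-event rate, so the rates below are assumptions.

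**Step 1. Reproduce the plan's figures.** 300 × 0.38 = 114, and 114 / 3 = 38. The two-proportion power formula with pooled variance, 38 per arm and two-sided 0.05, gives 0.886 for 75% vs 40% (stated: 88%) and 0.997 for 80% vs 30% (stated: above 99%). The 4-event threshold is also right at this size: an unstratified Miettinen and Nurminen test gives p = 0.079 for 3 vs 0 events and p = 0.041 for 4 vs 0.

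**Step 2. Time before re-treatment.** With flare-free proportion S at 12 months and a constant flare hazard h = −ln S per year, mean time before re-treatment is 12(1 − S)/h months.

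- PBO, S = 0.30: h = 1.204; 12 × 0.70 / 1.204 = 6.98 months (38 subjects: 22.1 subject-years).
- GLM QM, S = 0.80: h = 0.223; 12 × 0.20 / 0.223 = 10.76 months (34.1 subject-years).
- Ratio PBO/QM: 6.98 / 10.76 = 0.65.

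The same formula gives a ratio of 0.75 at 40%/75%, 0.56 at 20%/80% and 0.84 at 40%/60%. If flares at 30%/80% are instead spread uniformly over months 2 to 6 or months 4 to 10, the ratio is 0.62 or 0.77. The imbalance does not depend on the constant hazard.

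**Step 3. Percentages before re-treatment when true rates are equal.** For event rate r per year, P(event before re-treatment) = r/(r + h) × (1 − exp(−(r + h))).

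| r per year (assumed) | PBO, 30% flare-free | QM, 80% flare-free | QM/PBO | PBO, 40% | QM, 75% |
|---|---|---|---|---|---|
| 0.1 | 5.6% | 8.5% | 1.53 | 6.3% | 8.3% |
| 0.5 | 24.0% | 35.6% | 1.48 | 26.7% | 34.6% |
| 1.0 | 40.4% | 57.7% | 1.43 | 44.5% | 56.2% |

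An exposure-adjusted rate ratio would be 1.0 in every row. If a two-sided 5% comparison of percentages were made in this window, the chance of a nominally significant difference with equal rates would be about 19% at r = 0.5 and 32% at r = 1.0 (30%/80%, 38 per arm, normal approximation).

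**Step 4. Whole Period 2.** Placebo time on open-label golimumab: 12 − 6.98 = 5.02 months, or 42% (4.14 months, or 35%, at 40% flare-free).

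**Step 5. If golimumab truly doubled a rate, 0.1 to 0.2 per year (30%/80%).**

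| View | PBO | QM | QM/PBO |
|---|---|---|---|
| No switching | 9.5% | 18.1% | 1.90 |
| Whole Period 2 | 13.2% | 18.1% | 1.38 |
| Before re-treatment | 5.6% | 16.3% | 2.92 |

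As measures of the on-drug against off-drug contrast, the two planned views depart from it in opposite directions.

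**Simplifications.** Re-treatment starts at flare; dropout, carry-over of Period 1 golimumab and the added re-treatment course after first flares in Months 19 to 22 are ignored.

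**The case against.** A reader might infer that the plan mixes open-label events into the placebo column and never separates them. The documents do not support that: Section 8.6.2 plans a before/after re-treatment summary, which does the separating. What the split lacks is a time denominator.

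A reader might also infer that the whole-Period-2 comparison is contaminated and should lose its p-value. That does not follow either. Section 4.3 describes a treatment paradigm that includes restarting golimumab after a flare. Comparing groups over all of Period 2 measures withdraw-and-re-treat against continue, keeps the benefit of randomisation, and has roughly equal follow-up. A smaller difference in that view is part of the strategy's effect. Nor does the plan choose to ignore the switch in Tiers 1 and 2; it is silent on the window.

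Three further points stand in part:

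- **Switching share.** The 42% is an upper figure for the 30% flare-free scenario. Section 8.6.1 counts discontinuations as flares and allows for subjects who flare without being re-treated.
- **Stakes.** No safety hypothesis is stated, and Section 8.6.2 calls the intervals descriptive. At 0.1 events per year the expected counts before re-treatment are 38 × 0.056 = 2.1 and 38 × 0.085 = 3.2 subjects, below the 4-event trigger on average. The broad Tier 2 categories are reported regardless, and a descriptive estimate can still mislead.
- **Limits of rates.** The last Period 1 dose is at Month 9, and Section 8.12 itself notes the long half-life. Early placebo time therefore follows recent golimumab, and cutting at re-treatment gives that phase more weight. Exposure-adjusted rates do not remove this and assume a roughly constant hazard. These limits should be stated beside the rates. They do not make crude percentages over unequal time preferable.

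**Conclusion.** The point holds for the before-re-treatment window. Under the plan's 30%/80% assumption, placebo has about 0.65 of the time at risk of monthly golimumab (0.75 at 40%/75%). Equal event rates would then show about 1.4 to 1.5 times the percentage on golimumab at 30%/80%. No planned adverse-event analysis adjusts for this. The subject-time in Section 8.12 could not be used as it stands, because its stated stop at re-treatment applies to placebo only. Section 8.6.2 defers no adverse-event method to the supplemental SAP.

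The whole-Period-2 comparison is a legitimate strategy comparison. The plan needs only to label it so and to say that it is the window for Tiers 1 and 2.

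The sizes rest on the plan's flare-free proportions, a constant flare hazard, assumed event rates and the simplifications listed in the working. The direction holds whenever flares are more frequent on placebo. This is a cheap improvement to a secondary, largely descriptive analysis and does not affect the primary efficacy result.

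**What to change.** In Section 8.6.2:

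1. Keep the whole-Period-2 comparison by treatment group, label it as a treatment-strategy comparison, and state that this window feeds the Tier 1 test and the Tier 2 intervals.
2. For the before-re-treatment window, add exposure-adjusted incidence (events per 100 subject-years, rate difference with 95% interval) for Tier 1 events and the broad Tier 2 categories. Cut events and subject-time at the first open-label re-treatment dose, by the same rule in all three arms.
3. Report events after re-treatment separately.
4. Note beside the rates that early placebo time carries over Period 1 golimumab and that the rates assume a roughly constant hazard.

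In Section 8.12, align the subject-time definitions of the three groups for this purpose.

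The cost is SAP wording and one extra set of tables from dates already collected. The added tables will have fewer events and wider intervals than the whole-period ones.
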